Visit Timing	Vac 1	Vac 1 +14 d	Vac 1 +28 d	End of 1 st RSV Season	Vac 2	Vac 2 +14 d	Vac 2 +28 d	Vac 2 +84 d	Vac 2 +24 we	End of 2 nd RSV Season	Vac 2 +52 we/			
Visit Month	0				12		13	15	18		24			
Visit Day	1	15 ^b	29 ^b		365 ^b	379 ^b	393 ^b	449 ^b	533 ^b		730 ^b			
Visit Window		+3 d	+3 d	+35 d	±2 mo	+3 d relative to Vac 2	+3 d relative to Vac 2	+7 d relative to Vac 2	+14 d relative to Vac 2	7/+14 d	±1 mo relative to Vac 2 ^{cc}			
Revaccination Subcohort 1A (N=120)														
Midturbinate nasal swab kit training and distribution	●	● ^q			● ^q									
Thermometer training and distribution	●				●									
Ruler training and distribution	●				●									
Verification of selected eligibility criteria					● ^r									
Contraindications to vaccination					● ^t									
Vaccination	●				●									
30 minute post vaccination observation ^s	●				●									
Solicited AE recording ^t	●				●									
Unsolicited AE recording ^u		Continuous				Continuous								
SAEs ^v		Continuous until the end of the first RSV season (or 6 months after vaccination, whichever comes later), and from revaccination on Day 365 until the end of the second RSV season (or 6 months after vaccination, whichever comes later) ^{dd}												
AEs and special reporting situations related to study procedures and non investigational (concomitant) Janssen products		Continuous until the end of the participant's study participation												
AEs leading to discontinuation (from study)		Continuous until the end of the participant's study participation												
Concomitant medications ^{w,x}		Continuous until the end of the participant's study participation ^y												
ARI surveillance ^z		Twice per week via the eDiary from vaccination on Day 1 until the end of the first RSV season, and from revaccination on Day 365 until the end of the second RSV season												
eDiary review of solicited AEs by study staff	●				●									
Experience Survey				● ^{bb}										
Humoral immunity sample, mL	● 15 ^{aa}	15 ^{aa}			● 15	15	15	15	15		15			
Blood Draw Volumes														
Approx. daily blood draw, mL	15	15			15	15	15	15	15		15			
Approx. cumulative blood draw, mL	15	30	30	30	45	60	75	90	105	105	120			

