From vaccination on Day 1 until the end of the first RSV season, from the Day 365 (Month 12) visit until the end of the second RSV season, from the end of the second RSV season until the Day 730 (Month 24) visit, and from the Day 730 visit until the end of the third RSV season, all participants will be followed-up twice per week to monitor for symptoms that could indicate an ARI, as described in Section 9.1.1, [Overview](#). For participants in the Revaccination Subcohorts, follow-up of ARIs will stop at the end of the second RSV season for Subcohort A, at the Day 730 (Month 24) visit for Subcohort B, and at the latest at the end of the third RSV season for Subcohort C.

Each participant will be asked twice each week if they have experienced any ARI-like symptoms since the previous eDiary completion, or for participants that have one or more of these symptoms at baseline, if they have experienced any additional ARI symptoms or a worsening of their baseline symptoms ([Attachment 4](#)).

Symptoms and impact of an ARI will be assessed on a daily basis in all participants with an ARI episode, using the RiiQ Symptom Scale ([Attachment 5](#)) and the RiiQ Impact on Daily Activities Scale ([Attachment 11](#), as part of the Combined Impact Assessment), respectively, in the eDiary. The eDiary will also ask participants to complete the Patient Global Impression of Health (PGI-H), the Patient Global Impression of Severity (PGI-S), the Patient Global Impression of Change (PGI-C), and the Return to Usual Health question ([Attachment 7](#), as part of the Combined Impact Assessment) after they complete the RiiQ Symptom Scale and RiiQ Impact on Daily Activities Scale. (Note that the PGI-C and the Return to Usual Health question will not be completed on ARI Day 1). The eDiary ARI assessment asks participants to record thermometer logs.

The participants will additionally complete all 4 scales of the RiiQ v2 ([Attachment 6](#)) on the site's eDevice during the study visits at ARI Days 3-5 and ARI Day 29 (± 7 days), and each of the PGI scales and the Return to Usual Health question on the site's eDevice during the study visit at ARI Day 29 (± 7 days). Refer to Section [9.2.1.1, Patient-Reported Outcomes](#) for details.

Impact of an ARI on basic functioning will also be assessed by the study staff during study visits using the Lawton-Brody IADL assessment ([Attachment 8](#)).

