- The Per-protocol Efficacy (PPE) population will include all randomized and vaccinated participants excluding participants with major protocol deviations expecting to impact the efficacy outcomes. The list of major protocol deviations to be excluded from the efficacy analysis will be specified in the SAP or major protocol deviation criteria document which will be finalized before database lock and unblinding. Any participant with an RT-PCR-confirmed RSV-mediated ARI with onset within 14 days after vaccination will be excluded from the PPE population. Participants who discontinue within 14 days after vaccination will be excluded from the PPE population as well.

The PPE population is the primary efficacy population. Sensitivity efficacy analyses will also be performed on the FAS. For exploratory efficacy analyses focusing on data from the second

^a The specification of this subset for analysis of solicited and unsolicited AEs does not preclude the investigator from reporting an AE in any participant if he/she considers the event to be of clinical relevance and/or related to the study vaccine.

RSV season only, the participants of Revaccination Subcohort A will be additionally excluded. For analyses focusing on data from the third RSV season, participants of Revaccination Subcohorts A and B will be excluded. For exploratory efficacy analyses focusing on data over 2 RSV seasons, the second RSV season data will be excluded for the participants of Revaccination Subcohort A. For analyses focusing on data over 3 RSV seasons, second and third RSV season data will be excluded for the participants of Revaccination Subcohort A, and third RSV season data will be excluded for participants of Revaccination Subcohort B. Participants who develop major protocol deviations expecting to impact the efficacy outcomes and occurring up to the considered RSV season will be **additionally** excluded from the PPE when focusing on data including the second or third RSV season.

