11.4.3.1. Analysis

For endpoints that intend to explore VE, an exact Poisson regression model will be fitted in a similar way as for the primary endpoint. The 95% 2-sided CI for the VE (1-relative risk rate) will be calculated from the regression model described above.

For exploratory endpoints regarding only season 2 data, the follow-up time for cases in season 2 is defined as the time between the Day 365 (Month 12) visit and the occurrence of the first event (according to the considered endpoint) in the considered season, for non-cases in season 2, it is the time between the Day 365 visit and the end of the second season visit. However, for participants that discontinued before the end of the second season and had an event in Season 2 (according to the considered endpoint), the follow-up time is defined as the time between the Day 365 visit and the occurrence of the first event and for participants that discontinued before having an event in season 2, follow-up time is the time between the Day 365 visit and the date of last contact. Participants that discontinued prior to the Day 365 visit as well as participants that are part of Revaccination Subcohort A will be excluded from the analysis.

For exploratory endpoints regarding only Season 3 data, the follow-up time for cases in Season 3 is defined as the time between the Day 730 (Month 24) visit and the occurrence of the first event (according to the considered endpoint) in the considered season, for non-cases in Season 3, it is the time between the Day 730 visit and the end of the third season visit. However, for participants that discontinued before the end of the third season and had an event in Season 3 (according to the

considered endpoint), the follow-up time is defined as the time between the Day 730 visit and the occurrence of the first event and for participants that discontinued before having an event in Season 3, follow-up time is the time between the Day 730 visit and the date of last contact. Participants that discontinued prior to the Day 730 visit as well as participants that are part of Revaccination Subcohorts A and B will be excluded from the analysis.

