For exploratory endpoints over 2 seasons (Season 1 and Season 2), the follow-up time is defined as the time between the Day 1 vaccination and the occurrence of the first event (according to the considered endpoint) in the first 2 seasons, for non-cases, it is the time between the Day 1 vaccination and the end of the second season visit. However, for participants that discontinued before the end of the second season and had an event (according to the considered endpoint), the follow-up time is defined as the time between the Day 1 vaccination and the occurrence of the first event and for participants that discontinued before having an event, follow-up time is the time between the Day 1 vaccination and the date of last contact. For Revaccination Subcohort A participants, only the first season is taken into account: for cases during the first season, the follow-up time is the time between the Day 1 vaccination and the occurrence of the first event (according to the considered endpoint), for non-cases it is the time between the Day 1 vaccination and end of first season visit.

For exploratory endpoints over 3 seasons (Season 1, 2 and 3), the follow-up time is defined similar as for endpoints over 2 seasons, but data up to the end of the third season are taken into account (instead only data up to the end of the second RSV season). For Revaccination Subcohort A participants, only the first season is taken into account and follow-up time is defined similar as explained above. For Revaccination Subcohort B participants only the first 2 seasons are taken into account: for cases during the first 2 seasons, the follow-up time is the time between the Day 1 vaccination and the occurrence of the first event (according to the considered endpoint), for non-cases it is the time between the Day 1 vaccination and the end of second season visit.

For continuous endpoints, actual values and changes from baseline (if meaningful) will be summarized descriptively. Categorical endpoints will be tabulated.

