11.11. Safety Analyses

No formal statistical testing of safety data is planned. Safety data by vaccination group and based on the FAS will be analyzed descriptively. The analysis of solicited and unsolicited AEs will be restricted to a subset of the FAS (ie, the Safety Subset). For SAEs, the complete FAS is considered. The impact of baseline factors (eg, being at increased risk for severe RSV disease) might be explored as well. Additionally, the analysis of solicited and unsolicited AEs and AESIs (if collected) will also be performed for each of the Revaccination Subcohorts and will be restricted to participants of the Revaccination Subcohorts that are part of the FAS.

Adverse Events (Solicited and Unsolicited)

The verbatim terms used in the eCRF by investigators to report AEs will be coded using the Medical Dictionary for Regulatory Activities (MedDRA). All reported AEs with onset during the active vaccination phase (ie, AEs occurring after vaccination up to 28 days post-vaccination), and all SAEs and AESIs will be included in the analysis. For each AE, the number and percentage of participants who experience at least 1 occurrence of the given event will be summarized by group.

Solicited local (at the injection site) and systemic AEs will be summarized descriptively. The overall frequencies per group as well as frequencies according to severity and duration will be calculated for solicited AEs.

Summaries, listings, datasets, or participant narratives may be provided, as appropriate, for those participants who die, who discontinue the study (or study vaccination, if applicable) due to an AE, or who experience a severe AE, an SAE, or an AESI.

Any ARI recorded as an (S)AE in the eCRF will be excluded from any AE analysis if the laboratory RT-PCR is subsequently found to be positive for RSV. ARIs arising from RSV infection will not be reported as (S)AEs in the Clinical Study Report as they are endpoints of the study and will be tabulated separately.

Vital Signs

A tabulation of the distribution of temperatures in the 7 days after vaccination, per half degree intervals, will be provided. For systolic and diastolic blood pressures, pulse rate and respiratory rate, the percentage of participants with values beyond clinically relevant limits will be summarized.

Physical Examination

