- During the entire study, (S)AEs and special reporting situations related to study procedures or to non-investigational (concomitant) Janssen products will be reported from the time a signed and dated informed consent form (ICF) is obtained onwards until the end of the study period for each participant.

The (S)AE listing in the eCRF will not be updated based on the RSV RT-PCR results and will remain listed on the eCRF as ARIs.

For Revaccination Subcohort A, all SAEs will be reported from administration of study vaccine on Day 1 until the end of the first RSV season (or 6 months after vaccination, whichever comes later), and from the time of revaccination at Month 12 until the end of the second RSV season, or until 6 months after revaccination, whichever comes later. For Revaccination Subcohort 2A, all SAEs and AESIs will also be collected from the time of revaccination on Day 730 until 6 months after revaccination. For Revaccination Subcohorts B and C, all SAEs and AESIs will be collected from the time of revaccination until 6 months thereafter. Collection of SAEs associated with ARIs and complications related to ARIs that classify as SAEs will stop at the end of the second RSV season for Subcohort A, on Day 730 (Month 24) for Subcohort B, and at the latest at the end of the third RSV season for Subcohort C.

For all Revaccination Subcohorts, SAEs classified as related to the study vaccine, SAEs resulting in death, (S)AEs leading to discontinuation from the study, and (S)AEs and special reporting situations related to study procedures or to non-investigational (concomitant) Janssen products will be collected during the entire study for all participants. For the participants in the Revaccination Subcohort C, these (S)AEs will be collected retrospectively for the time period between the last end of the RSV season visit and the revaccination upon the day of revaccination.

From the time of local approval of protocol amendment 6 onwards, TTS is considered to be an AESI. Thrombotic events and/or thrombocytopenia (defined as platelet count below 150,000 cells/mm³) are considered to be potential AESIs. All AESIs, including potential AESIs, will be reported to the sponsor from the moment of revaccination until 6 months after revaccination.

The sponsor will evaluate any safety information that is spontaneously reported by an investigator beyond the time frame specified in the protocol.

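### Section 11.11 takes RSV-positive ARIs out of Subcohort A's AE and SAE summaries after its Day 365 active dose, although no VE analysis counts those events

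*Protocol*

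**What the plan says.** **The safety rule.** Protocol section 11.11, repeated in the synopsis, states that an ARI recorded as an (S)AE "will be excluded from any AE analysis if the laboratory RT-PCR is subsequently found to be positive for RSV". RSV ARIs are not to be reported as (S)AEs in the study report "as they are endpoints of the study and will be tabulated separately". Neither place limits the rule by season, dose or subcohort. Section 11.11 also provides for AE analyses in each Revaccination Subcohort.

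**The efficacy rules for Subcohort A.** Section 11.1 removes these participants from the season 2 and season 3 analyses. For the analysis over two seasons, "the second RSV season data will be excluded for the participants of Revaccination Subcohort A"; over three seasons, both later seasons are dropped. Section 11.4.3.1 agrees. For season 2, "participants that are part of Revaccination Subcohort A will be excluded from the analysis". For the multi-season analyses, "For Revaccination Subcohort A participants, only the first season is taken into account".

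**Data collection after the Day 365 dose.** The Schedule of Activities for Subcohort 1A runs ARI surveillance "until the end of the first RSV season, and from revaccination on Day 365 until the end of the second RSV season", and the schedule for 2A does the same. Section 3.1 confirms that "follow-up of ARIs will stop at the end of the second RSV season for Subcohort A". Section 12.3.1 collects all SAEs "from the time of revaccination at Month 12 until the end of the second RSV season, or until 6 months after revaccination", whichever is later. Under section 9.2.4.1, every ARI in the 28 days after revaccination, serious or not, is recorded as an AE.

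**The endpoints concerned.** Section 2.1 lists unsolicited AEs for 28 days after revaccination, and SAEs during the RSV season, as secondary endpoints.

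**The concern.** Taking endpoint events out of AE tables is reasonable where the efficacy analysis shows them. In Subcohort A after Day 365 it does not. Both 1A and 2A have then had active vaccine, so the plan rightly keeps their later events out of VE. The efficacy rules were adapted to this subcohort and the matching safety rule was not.

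At stake is what a reader of Subcohort A's own safety results sees. Section 11.12 describes its 28-day and final analyses as covering safety and immunogenicity data. An RSV ARI dropped from the AE and SAE summaries has no named place in those reports, even if it was serious or fatal. RSV illness soon after an active dose of an RSV vaccine is something a safety reader would look for.

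**Working it through.** The protocol states no figure for this point. The check is a comparison of rules, followed by arithmetic for scale.

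**Where the rule acts in Subcohort A**

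| Event after the Day 365 dose, up to the end of season 2 | Recorded as (S)AE? | Removed by 11.11 if RSV-positive? | Counted for VE? |
|---|---|---|---|
| Any ARI within 28 days | Yes, as an AE (9.2.4.1) | Yes | No |
| Serious ARI at any time | Yes, as an SAE (12.3.1) | Yes | No |
| Non-serious ARI after 28 days | No | Nothing to remove | No |
| Complication recorded as its own (S)AE | Yes | Not by the wording, which names ARIs only | No |

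The first two rows carry the point. It is confined to Subcohort A because ARI follow-up ends at Day 730 for Subcohort B and by the end of season 3 for C, so it does not continue past their revaccinations. It also ends before the third dose in 2A. Study RT-PCR results would not normally trigger the exclusion in those settings.

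**Scale: inputs**

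- n = 240, or 120 per group (sections 5 and 11.2.4).
- Placebo incidence of Case Definition #2: 0.75% per season; planning VE: 70% (section 11.2.1).
- Season length 5 to 7 months of 30.4 days with even risk. This is an assumption; the protocol gives no such figure.

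The formula 1 − (1 − p)^240 gives 21%, 70% and 91% at true rates of 0.1%, 0.5% and 1%, matching Table 10 for Subcohorts A and C.

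**Whole season, an upper scale only**

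- No protection: 240 × 0.0075 = 1.8 cases; chance of at least one = 1 − (1 − 0.0075)^240 = 84%.
- 70% VE: 1.8 × 0.3 = 0.54 cases; chance of at least one = 1 − (1 − 0.00225)^240 = 42%.
- Per group of 120: 0.27 to 0.90 cases.

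**First 28 days, where every ARI is an AE**

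- Share of a 5-month season: 28 / 152 = 0.184. Share of a 7-month season: 28 / 212.8 = 0.132.
- Low end: 0.54 × 0.132 = 0.07 cases. High end: 1.8 × 0.184 = 0.33 cases.
- Chance of at least one (Poisson): 1 − exp(−0.07) = 7% to 1 − exp(−0.33) = 28%.

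**Serious ARIs to the end of season 2.** The protocol gives no serious fraction, so no count can be derived.

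**Direction of error.** Section 11.2.1 assumes vaccination before the season. If Day 365 also falls before it, even risk overstates the 28-day share. Section 11.12 allows for a second season with few or no RSV cases, which would lower every figure. Conversely, Case Definition #2 is the only incidence given, and RSV-positive ARIs of any severity would be more frequent.

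**The case against.** The strongest reply is that the same passage of 11.11 already deals with these events: RSV ARIs go into a separate table, and nothing bars Subcohort A from it. The end-of-season-2 analysis takes in all efficacy and safety data and, if cases are few, may list RSV-positive participants. A reader might infer from the point above that RSV illness after revaccination disappears from the study. The text does not support that. The events are moved, and the (S)AE entry stays in the eCRF whatever the RT-PCR result. What remains is that the table is study-wide and is not tied to Subcohort A's safety reports.

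Second, being a study endpoint is wider than being counted in a VE model. Viral load, medical resource use and the CEC severity review can also draw on these events. Repeat main-cohort episodes leave the AE tables too, although only the first per season counts for VE. This stands, so it would go too far to say the rule's rationale is simply false. The narrower statement holds: no VE analysis shows these events for Subcohort A.

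Third, complications such as pneumonia or a COPD exacerbation, if recorded as separate (S)AEs, are not covered by the wording. This also stands.

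Fourth, a reader might take 42% to 84% as the chance that an event goes missing. It is not. Most whole-season cases would be non-serious ARIs more than 28 days after the dose, which are never recorded as AEs.

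Fifth, 11.11 analyses SAEs on the complete FAS, and one uniform rule avoids mixed definitions and double display. That is a real cost of any exemption, but a footnote can carry it.

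Leaving the matter to the SAP does not answer the point. The protocol fixes an unconditional rule, and an SAP that kept these events in Subcohort A's tables would contradict it.

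**Conclusion.** The point holds in limited form. As written, 11.11 would leave RSV-positive ARIs after the Day 365 dose out of Subcohort A's 28-day unsolicited-AE and SAE summaries, and so understate two secondary safety endpoints in an actively revaccinated group. The events would appear only in a study-wide RSV tabulation.

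The size is small: about 0.07 to 0.33 Case Definition #2 cases in the 28-day window, plus an unknown number of serious ARIs up to the end of season 2. The 28-day range rests on the protocol's 0.75% incidence, protection between none and 70%, and even risk over 5 to 7 months. The whole-season range of 0.54 to 1.8 cases is only a ceiling for scale.

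The documents do not support reading this as a failure of safety oversight. Expedited reporting and IDMC review do not depend on the rule, no safety hypothesis is tested, and section 1.1 does not expect enhanced disease in adults aged 60 or older. Severity is low.

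**What to change.** Add one sentence to 11.11, and to the matching synopsis text: the exclusion does not apply to ARI (S)AEs with onset after revaccination in Subcohort A. These stay in that subcohort's AE, SAE and death summaries, flagged as RSV-positive, and also appear in the separate RSV tabulation.

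Add a footnote to the affected tables saying that Subcohort A follows a different rule from the main cohort and that the flagged events are shown twice.

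Leave the main-cohort rule unchanged. Tying the exclusion to events counted for efficacy would look tidier, but it would return repeat main-cohort episodes to the SAE tables.

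The cost is the sentence, the flag, the footnote and the double display. No new data are needed.
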